2.10 Section 8.5.2 Hypoglycaemic episodes

Plasma glucose should always be measured and recorded when a hypoglycaemic episode is suspected.

All plasma glucose values:

- \leq 3.9 mmol/L (70 mg/dL) or
- > 3.9 mmol/L (70 mg/dL) occurring in conjunction with hypoglycaemic symptoms

5th bullet:

• Date, time, and dose of last trial product (and other anti-diabetic treatment, except between V32 and V33) administration prior to the episode

2.11 Section 8.5.5 Electrocardiogram (ECG)

A 12-lead ECG must be performed. by the investigator or delegated staff. The ECG must be interpreted, signed and dated by the investigator to verify that the data has been reviewed prior to determining the eligibility of the subject. The ECG at screening must be done at the latest at V2 and the results interpreted by the investigator prior to determine the eligibility of the subject. can be obtained at the latest at V2. The result of the ECG must be available to the investigator prior to randomisation. The ECG must not be obtained more than 2 weeks prior to V2; in that case a reassessment is necessary.

2.12 **Section 8.6.1 Questionnaires**

The investigator or site staff are only allowed to fill in the headings of the questionnaires.

The investigator or site staff should eheck review the questionnaire for empty fields and potential adverse events in the questionnaires when returned by the subject. Review of the questionnaires must be documented either on the documents and/or in the subject's medical record.

Protocol Amendment 2
Trial ID: NN9068-4229
UTN:U1111-1168-9343
Date: Versic Versic Status

 Date:
 28 November 2016
 Novo Nordisk

 Version:
 1.0

 Status:
 Final

 Page:
 13 of 19

2.13 Section 9.1 Trial products

EudraCT No.: 2015-001596-48

During the 26-weeks treatment period and the 4 weeks follow-up period; the patients de-facto cost (actual patient cost, not covered by the Health Authorities/any insurance) of SGLT2i and metformin (mono- or fixed dose combination products) *can* will be reimbursed in accordance with local legislation and Ethics Committee approval. Pioglitazone will not be reimbursed.

2.14 Section 9.4 Drug accountability and destruction

Drug accountability of all trial products *received at site* is the responsibility of the investigator.

2.15 Section 12.1 Definitions

Serious adverse event

The following adverse events must always be reported as a SAE using the important medical event criterion if no other seriousness criteria are applicable:

- suspicion of transmission of infectious agents via the trial product
- risk of liver injury defined as ALT or AST > 3 x upper normal limit and total bilirubin > 2 x upper normal limit, where no alternative aetiology exists (Hy's law)

Major adverse cardiovascular event

A major adverse Any cardiovascular event (MACE) is any AE which can be categorised into the following groups will be evaluated as a potential Major Adverse Cardiovascular Event (MACE):

- Cardiovascular Death
- Mvocardial Infarction
- Hospitalisation for Unstable Angina
- Transient Ischemic Attack and Stroke
- Heart Failure Event (requiring hospitalisation)
- Cardiac procedures
 - Interventional Cardiology
 - o Peripheral Vascular Intervention
 - Stent Thrombosis

A MACE is defined as:

- Cardiovascular Death
- Non-fatal Myocardial Infarction
- Non-fatal Stroke

CONFIDENTIAL

Date: Version: Status: Page:

28 November 2016 | Novo Nordisk Final 14 of 19

2.16 Section 12.2 Reporting of adverse events

All events meeting the definition of an AE must be collected and reported. This includes events from the first trial-related activity after the subject has signed the informed consent until the end of the two post-treatment follow-up periods. Please be aware that hypoglycaemic episodes should not be reported before any trial drug is given e.g. hypoglycaemic episodes should be reported from the randomisation visit (V2). Subjects discontinuing trial product prematurely (see section 6.4) will be contacted every 4th week and asked for information about antidiabetic medication, MACE and SAEs. These subjects should finally come in for a V32A at week 26, only to assess antidiabetic medication, MACE, SAEs, fasting body weight and a blood sample to measure HbA_{1c}.

2.17 Section 12.5.1 Pregnancies in female subjects

Forms and timelines for reporting AEs:

Non-serious AEs:

Paper AE form* within 14 calendar days of the investigator's first knowledge of the initial or follow-up information to the non-serious AE.

SAEs:

- Paper AE form* within 24 hours of the investigator's first knowledge of the SAE
- Paper SIF within 5 calendar days of the investigator's first knowledge of the SAE
- SAE follow-up information to the AE form and/or SIF within 24 hours of the investigator's first knowledge of the follow-up information

2.18 Section 13.2 Case report form flow

The SMPG measurements and corresponding trial drug doses for titration purpose should must be entered within 24 hours after the site visit/phone contact throughout the trial.

2.19 Section 17.3.1 Primary statistical analysis primary estimand

Multiple imputation – unconditional jump to reference – retrieved data – NI penalty

The primary estimand will be estimated based on the FAS using all post baseline HbA_{1c} measurements obtained at planned visits up to and including week 26, and data retrieved at week 26 (V32A) from subjects prematurely discontinued from randomised treatment. To estimate this estimand for evaluation of non-inferiority of HbA_{1c}, a pattern mixture model approach³⁵ will be

^{*} It must be clearly stated in the AE diagnosis field on the AE form if the event occurred in the subject, foetus or newborn infant. If the AE occurred in the foetus or newborn infant, the AE can only be reported on paper AE and SIF.

CONFIDENTIAL

Date: Version: Status: Page:

28 November 2016 | Novo Nordisk Final 15 of 19

adopted based on sequential modelling using the conditional approach described generally in section 7.3.1 and the conditional approach specifically in section 7.4.2 in the book by O'Kelly and Ratitch³⁵. A penalty in terms of the NI margin is added to withdrawn or prematurely discontinued subjects in the IDegLira arm. It mimics an ITT scenario where withdrawn and prematurely discontinued subjects from the investigational treatment (IDegLira) arm not having a week 26 measurement are assumed to be switched to a treatment inferior to comparator (IGlar) or any other treatment received after premature treatment discontinuation. This corresponds to a jump to reference (J2R) principle where a penalty in terms of the NI margin is added to withdrawn or prematurely discontinued subjects in the IDegLira arm. Observe that the imputation method J2R principle and use of retrieved (V32A) data in analyses will equalise treatment effects and in turn assay sensitivity in the non-inferiority setting may be jeopardized. The penalty of the non-inferiority margin³⁶ is to remedy this. Multiple copies (1000 copies) of the full dataset will be generated by imputing missing values based on estimated parameters for a subgroup of subjects in the trial.

2.20 Section 17.3.2 Sensitivity analyses primary estimand

Multiple imputation – conditional jump to reference – retrieved data – NI penalty

The analysis is similar to the primary analysis except that observed values for prematurely discontinued IDegLira subjects are not set missing (step 1 is left out). Observe that for IDegLira now only missing data after premature discontinuation are imputed by the sequential ANOVAs (step 3 to 5) and this corresponds to the conditional sequential modelling approach described in section 7.4.3 in the book by O'Kelly and Ratitch³⁵ principle is named copy reference (CR); intermittent missing data are imputed by MCMC (step 2).

Multiple imputation – unconditional jump to reference – retrieved data – NI penalty – tipping point

Multiple imputation – unconditional jump to reference – retrieved data – NI penalty – CAS Multiple imputation – unconditional jump to reference – retrieved data – NI penalty – PP

2.21 Section 17.4.1.1 Primary statistical analyses primary estimand

Body weight - multiple imputation - unconditional - retrieved data

The change from baseline in body weight after 26 weeks will be analysed with the *multiple* imputation unconditional sequential 12R pattern mixture model for HbA_{1c}, substituting body weight for HbA_{1c} and leaving out the non-inferiority penalty (step 6).

CONFIDENTIAL

Date: Version: Status: Page:

28 November 2016 | Novo Nordisk 1.0 Final 16 of 19

Treatment-emergent hypoglycaemic episodes – multiple imputation – method 1

The number of hypoglycaemic episodes will be analysed using a multiple imputation technique for count data under the J2R principle as follows.

Glycaemic control – multiple imputation – unconditional – retrieved data

The change from baseline in HbA_{1c} after 26 weeks will be analysed with the *multiple imputation* unconditional sequential J2R pattern mixture model for HbA_{1c} but leaving out the non-inferiority penalty (step 6).

Insulin dose – multiple imputation – unconditional – retrieved data

The insulin dose after 26 weeks will be analysed with the multiple imputation unconditional sequential J2R pattern mixture model for HbA_{1c}, substituting insulin dose for HbA_{1c}, leaving out the non-inferiority penalty (step 6) and using baseline HbA_{1c} as covariate as there is no baseline dose.

2.22 Section 17.4.1.2 Sensitivity analyses primary estimand

Continuous endpoints, body weight, HbA_{1c} and insulin dose – multiple imputation – conditional copy reference retrieved data

These analyses are repeats of the primary analyses using the *conditional approach* CR principle in place of the *unconditional approach* J2R principle, just as for the *conditional* CR sensitivity analysis of the primary estimand of the primary objective.

Continuous endpoints body weight, HbA_{1c} and insulin dose – multiple imputation – unconditional jump to reference retrieved data - tipping point

Count endpoint hypoglycaemic episodes – multiple imputation – method 2 copy reference

This is a repeat of the primary analysis using the CR principle in place of the J2R principle. More specifically, in In this analysis IDegLira subjects are assumed to have the event rate of the IDegLira arm prior to premature discontinuation and the event rate of IGlar after premature discontinuation. The method follows method 1 the multiple imputation J2R for count data above, but in the second step pre discontinuation rates are the respective groups rates whilst post discontinuation rate is the rate of comparator (IGlar).

Count endpoint hypoglycaemic episodes – multiple imputation – method 1 jump to reference tipping point

This is a repeat of *method 1*the multiple imputation J2R above, now varying a penalty on the post discontinuation event rate until IDegLira is no longer superior to IGlar.

CONFIDENTIAL

Date: Version: Status: Page:

28 November 2016 | Novo Nordisk Final 17 of 19

2.23 Section 17.4.1.4 Sensitivity analyses secondary estimand

Continuous endpoints body weight, HbA1c and insulin dose - multiple imputation unconditional jump to reference retrieved data

2.24 Section 17.4.2.1 Efficacy endpoints

For each of the multiple copies (1000) of the full dataset of the primary analysis of the primary estimand (unconditional multiple imputation J2R with retrieved data, NI penalty section 2.19) the responder endpoints are derived without using the non-inferiority penalty (step 6) and analysed with the standard logistic regression model. Estimates are pooled using Rubin's rule³/.

Waist circumference change from baseline after 26 weeks

Change from baseline in waist circumference will be analysed by unconditional multiple imputation J2R.

Fasting plasma glucose change from baseline after 26 weeks

Change from baseline in FPG will be analysed by *unconditional* multiple imputation J2R.

Fasting lipid profile after 26 weeks

Cholesterol, LDL cholesterol, HDL cholesterol, VLDL cholesterol, triglycerides and free fatty acids will be analysed separately by *unconditional* multiple imputation—J2R. In these statistical analyses, the endpoint will be log-transformed and so will the corresponding baseline covariate.

Self-measured plasma glucose (SMPG) 9-point profile change from baseline after 26 weeks

A linear mixed effect model will be fitted to the 9-point SMPG profile data. The model will include treatment, pre-trial OAD, time (within 9-point profile), the interaction between treatment and time, the interaction between pre-trial OAD and time as fixed factors, and subject as random effect, where measurements within subjects will be assumed correlated as specified by a compound symmetric covariance matrix. From the model mean profile by treatment and relevant treatment differences will be estimated and explored.

Change from baseline in mean of the 9-point profile and prandial increment endpoints will be analysed separately by *unconditional* multiple imputation-J2R.

Blood pressure (systolic and diastolic) change from baseline after 26 weeks

Change from baseline in systolic and diastolic blood pressure will be analysed separately by unconditional multiple imputation J2R.

Protocol Amendment 2 Trial ID: NN9068-4229 UTN:U1111-1168-9343

EudraCT No.: 2015-001596-48

CONFIDENTIAL

Date: Version: Status: Page:

28 November 2016 | Novo Nordisk Final 18 of 19

2.25 Section 17.4.2.2 Safety endpoints

Hypoglycaemic episodes during 26 weeks

Number of nocturnal treatment-emergent severe or BG confirmed symptomatic hypoglycaemic episodes during 26 weeks will be analysed using the same (method 1) J2R multiple imputation model as used for the treatment-emergent severe or BG confirmed symptomatic hypoglycaemic episodes.

Pulse rate change from baseline after 26 weeks

Change from baseline in pulse rate will be analysed by *unconditional* multiple imputation—J2R.

2.26 Section 17.5 Health economics and/or patient reported outcomes

For each questionnaire, the summary scores will be summarised descriptively by visit and the change from baseline in score will be analysed separately by unconditional multiple imputation J2R.

2.27 Section 18.1 Benefit-risk assessment of the trial

Inclusion and exclusion criteria have been defined in order to ensure that only subjects that are eligible for trial participation are enrolled in the trial. Furthermore, withdrawal rescue criteria are defined to ensure that subjects are considered for withdrawal premature discontinuation of trial product, if the level of glycaemic control exceeds acceptable limits during trial participation.

2.28 Section 18.1.1.1 Identified risks

Acute gallstone disease

Cases of gallstones (cholelithiasis) and inflammation of the gallbladder (cholecystitis) have been reported from clinical trials with IDegLira. Both cholelithiasis and cholecystitis have possible clinical implications for the patients as the events might lead to hospitalisation and cholecystectomy. If cholelithiasis is suspected, treatment should be discontinued and gallbladder examination and appropriate clinical follow-up should be initiated. If acute gallstone disease is confirmed, the trial product must be permanently discontinued.

2.29 **Appendix A: Titration Guideline**

Section 3.1 Initiation of IDegLira or IGlar

For subjects randomised to IDegLira will the recommended start dose is on 10 dose steps, consisting of 10U insulin degludec/0.36 mg liraglutide once daily.

Protocol Amendment 2		Date:	28 November 2016	Novo Nordisk
Trial ID: NN9068-4229	CONFIDENTIAL	Version:	1.0	
UTN:U1111-1168-9343	CONFIDENTIAL	Status:	Final	
EudraCT No.: 2015-001596-48		Page:	19 of 19	

For subjects randomised to IGlar the recommended will start dose is on-10U of insulin glargine once daily.

Section 3.2 Titration of IDegLira or IGlar

The doses of IDegLira or IGlar should *must* be adjusted twice weekly on fixed days (Mondays and Thursdays).

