6.4 Premature discontinuation of trial product

All efforts should be made to keep the subject on trial product. Trial product must be discontinued if the subject meets rescue criteria or if the following applies:

 If the investigator suspects acute pancreatitis, all drugs suspected to relate to this condition must be discontinued until confirmatory tests have been conducted and appropriate treatment should be initiated

Trial product must be permanently discontinued if the following applies:

- Included in the trial in violation of the inclusion and/or exclusion criteria
- Pregnancy or intention to become pregnant
- Participation in other clinical trials throughout the trial
- In case the calcitonin value is ≥ 50 ng/L. Please see Appendix C
- Initiation or significant change in concomitant medications (in excess of 14 days) which in the investigator's opinion could affect weight or glucose metabolism
- Subjects that are diagnosed with acute pancreatitis (as a minimum 2 of 3: characteristic abdominal pain, amylase and/or lipase > 3x upper normal range or characteristic findings on ultrasound, computerised axial tomography /magnetic resonance imaging)

Permanent premature discontinuation of treatment with trial product will not lead to subject withdrawal from the trial. Trial product may be permanently discontinued at the discretion of the investigator due to a safety concern, unacceptable tolerability, or if a subject is judged to be non-compliant with trial procedures.

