8.1.7 Premature discontinuation of trial product

Subjects discontinuing trial product prematurely due to any of the rescue criteria (see section 6.5), criteria for premature discontinuation of trial product (see section 6.4) or at subjects own will, should be called in for an EoT visit corresponding to V32 as soon as possible after discontinuation of trial product, FU1 must be scheduled 7 days (+3 days) after discontinuation of trial product and FU2 must be scheduled 30 days (+3 days) after discontinuation of trial product.

Once the two follow-up contacts after discontinuation of trial product are completed the subject should be contacted by phone every 4 weeks. Information on antidiabetic medication and information on potential major cardiovascular events (MACE) and any SAEs occurring since last contact must be collected and recorded in the eCRF. Phone contacts must be documented in the medical record and in the eCRF. The subject should finally come in for a V32A at week 26 to report MACE, SAEs, total daily insulin dose, use of other antidiabetic medication, and have body weight measured and a blood sample taken to measure HbA_{1c}, see flow chart (section 2).

Final drug accountability must be done once the subject has discontinued the trial product and the premature discontinuation must be recorded in the IWRS through a treatment discontinuation session.

The reason for the premature discontinuation of trial product must be recorded in the eCRF.

Protocol Trial ID: NN9068-4229 UTN: U1111-1168-9343

EudraCT No.: 2015-001596-48

CONFIDENTIAL

Date: Version: Status: Page:

20 November 2015 | Novo Nordisk 2.0 Final 35 of 107

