18.1.1.2 Potential risks

Altered Renal Function

Dehydration due to known gastrointestinal effects associated with GLP-1 receptor agonists may in rare cases be associated with renal impairment in predisposed patients, and dehydration associated with treatment with SGLT2i could theoretically add to this risk. Patients treated with IDegLira should be advised of the risk of dehydration in relation side effects of GLP-1 receptor agonists and SGLT2i and take precautions to avoid fluid depletion. Furthermore, impaired renal function as defined in the protocol is an exclusion criterion in this trial. Monitoring of creatinine will be performed during the trial as part of standard safety laboratory surveillance.

Medullary Thyroid Cancer (C-Cell Carcinogenicity)

Thyroid C-cell carcinogenicity has been reported in rats and mice treated with GLP-1 receptor agonists in non-clinical studies. Based on these findings, monitoring of serum calcitonin will be performed approximately every 3 months in the present trial. Subjects with thyroid disease will be closely monitored and in case of elevated calcitonin a recommendation for follow-up is included in Appendix C in the protocol. Subjects with a personal or family history of medullary thyroid carcinoma and subjects with multiple endocrine neoplasia type 2 syndrome or/and subjects with a calcitonin value > 50 ng/L will be excluded from the trial.

Neoplasms

Epidemiologic evidence suggests that subjects with T2DM are at higher risk for many forms of cancer. Moreover, evidence from observational studies indicates that some medications used to treat hyperglycaemia are associated with either increased or reduced risk of cancer. It is thus important to demonstrate, that new antidiabetic therapies do not increase the inherent risk of neoplasms in the T2DM population.

Neoplasms will be followed closely. All neoplasms will be adjudicated externally by an EAC.

Pancreatic cancer

Pancreatic cancer is included as a potential risk, due to the focus on the potential association with GLP-1-based therapies. There is currently no support from non-clinical investigations or clinical trials that GLP-1 receptor agonists increase the risk of pancreatic cancer 42. GLP-1 receptor agonists treatment shall be withdrawn in patients with suspicion of/diagnosed pancreatic cancer and appropriate treatment and monitoring shall be initiated.

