2.2 Calcitonin \geq 50 and < 100 ng/L

Action: The subject (even if a screen failure) should be referred to a thyroid specialist for further evaluation and the trial product should be discontinued. The subject can remain in the trial however; all medications suspected to relate to this condition should be discontinued until appropriate treatment has been initiated.

Background: These values were found in 8 (0.14%) of the population of 5817 patients with thyroid nodular disease¹. Two of these subjects were diagnosed with MTC and two were diagnosed with C-cell hyperplasia, resulting in a positive predictive value of a C-cell anomaly of 50%.

Diagnostic evaluation should include:

- thyroid ultrasound examination
- if available no contraindication, a pentagastrin stimulation test. Subjects with positive pentagastrin stimulation tests should be considered to undergo surgery
- if pentagastrin is not available, thyroid ultrasound and fine needle aspiration biopsy may add important clinical information informing the need for surgery

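### Mandatory stops for gallstone disease and pancreatic cancer are missing from the section 6.4 list, and the calcitonin stop differs in force and permanence between 6.4 and Appendix C

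*Protocol*

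**What the plan says.** Section 6.4 first asks sites to try to keep subjects on trial product. It then gives the permanent stops under the line "Trial product must be permanently discontinued if the following applies". The items are eligibility violations, pregnancy or the intention to become pregnant, participation in another trial, calcitonin, certain changes in concomitant medication, and diagnosed acute pancreatitis. The calcitonin item reads "In case the calcitonin value is ≥ 50 ng/L. Please see Appendix C". A closing clause is permissive: "Trial product may be permanently discontinued at the discretion of the investigator due to a safety concern, unacceptable tolerability", or for non-compliance.

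Three other places also state stops:

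- Section 18.1.1.1, as changed by Amendment 2 (item 2.28), says treatment should be stopped when cholelithiasis is suspected, and then: "If acute gallstone disease is confirmed, the trial product must be permanently discontinued".
- Section 18.1.1.2 says of GLP-1 receptor agonists that "treatment shall be withdrawn in patients with suspicion of/diagnosed pancreatic cancer".
- Appendix C 2.2, for calcitonin from 50 to below 100 ng/L, says "the trial product should be discontinued". A following sentence adds that "all medications suspected to relate to this condition should be discontinued until appropriate treatment has been initiated". Appendix C 2.1, for 100 ng/L or more, uses must and refers back to 6.4.

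Section 8.1.7 starts the discontinuation procedures for subjects who stop under the rescue criteria, under 6.4, "or at subjects own will, should be called in for an EoT visit".

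**The concern.** An investigator who wants to know whether a subject has to come off trial product will naturally look in 6.4, the section on premature discontinuation. For confirmed gallstone disease or pancreatic cancer, that section offers at most a discretionary stop, preceded by an instruction to keep subjects on product. The benefit-risk chapter makes the same stops compulsory. For calcitonin, 6.4 sends the reader to Appendix C, and in the lower band the appendix is weaker than the section that points to it. No text says which wording prevails.

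What is at stake is consistent handling of safety stops across sites in a multinational, open-label trial. Two sites could treat the same finding differently, and each could cite the protocol.

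**Working it through.** No sample size, power or error rate is involved, so the check is a comparison of texts.

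| Event | Section 6.4 | Other text | Mismatch |
|---|---|---|---|
| Acute gallstone disease, confirmed | Not listed; discretionary clause only | 18.1.1.1 (Amendment 2): must, permanent | Mandatory against optional |
| Cholelithiasis, suspected | Not listed; discretionary clause only | 18.1.1.1 (Amendment 2): should | Absent from 6.4 |
| Pancreatic cancer, suspected or diagnosed | Not listed; discretionary clause only | 18.1.1.2: shall, worded for GLP-1 receptor agonist treatment | Mandatory against optional; reach in the glargine arm not stated |
| Calcitonin 50 to below 100 ng/L | Must, permanent | Appendix C 2.2: should, permanence not stated | Force and permanence |
| Calcitonin 100 ng/L or more | Must, permanent | Appendix C 2.1: must, permanence not stated | Permanence only |

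1. **Is the gallstone omission a change made elsewhere?** No. The change list of Amendment 2 goes from the flow chart to 6.5 and then 8.1.3, with no entry for 6.4. Its rationale (item 18) names section 18.1.1 alone. The same amendment did edit 6.5, 8.1.7 and 18.1. Amendment 1 changes only an exclusion criterion.

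2. **Does the protocol normally keep such stops out of 6.4?** No. Acute pancreatitis, the comparable risk in 18.1.1.1, also appears in 6.4, with one rule for suspicion and one for diagnosis. Gallstone disease and pancreatic cancer depart from that pattern.

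3. **Is the calcitonin threshold in conflict?** No. The stop begins at 50 ng/L in both places, and 6.4 and Appendix C 2.1 refer to each other. The difference is must against should in the lower band, and whether the stop is called permanent in either band.

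4. **Does Appendix C make the stop of trial product temporary?** It does not say so. In both bands the stop of trial product is a statement of its own without a time limit. The time limit is in the next sentence and concerns medications suspected of causing the condition. That could be read to include trial product, which is a further reason to state permanence.

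**The case against.** The best defence is that the benefit-risk chapter is part of the protocol and binds sites as much as 6.4 does. Nothing in 6.4 claims that its list is complete, so an investigator can obey both, and an added rule is not a contradiction. The gallstone stop was also issued openly, in an amendment for all countries with its own rationale item. This stands in part: a careful reader of the whole protocol would find the stops. It does not remove the difference in force, since 6.4 leaves optional what another binding section makes compulsory, and it does not answer the calcitonin wording.

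A reader might infer more than the documents support in three ways.

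- *That subjects stopped under the risk section fall outside 8.1.7 and lose their V32A data.* They do not. A stop for gallstones or pancreatic cancer is a safety-concern stop under 6.4, which 8.1.7 covers. Footnote 1 of the flow chart sends everyone who discontinues prematurely, whatever the reason, to V32, the two follow-ups and V32A. Section 12.2 also brings them to V32A, and 6.4 says that a permanent stop does not withdraw the subject from the trial.
- *That the primary estimand is affected.* It is defined regardless of whether subjects stay on assigned treatment. The 0.3% penalty in step 6 of the primary analysis goes to every prematurely discontinued IDegLira subject, under whichever section the stop was made. Uneven use of the stops could change who receives it, but through the penalty alone one subject more or fewer among 208 moves the arm mean by about 0.3/208 = 0.0014 percentage points. The documents give no frequency that would make this material.
- *That Appendix C says should at every value from 50 ng/L up.* It says must at 100 ng/L or more.

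**Conclusion.** The point holds as an inconsistency in the mandatory safety stops. Two stops that are compulsory in the benefit-risk chapter are missing from the operative list, and one listed stop is weaker in the appendix to which the list refers. No loss of follow-up data and no effect on the primary estimand is shown.

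Severity is low. That rests on the assumption that few subjects will have confirmed gallstone disease, suspected or diagnosed pancreatic cancer, or calcitonin of 50 ng/L or more on treatment; the documents give no rates with which to test it. The point is still worth correcting, because the rules concern subject safety and the change is to text only. This review takes no position on which rule is clinically right.

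**What to change.** Reconcile sections 6.4, 18.1.1.1 and 18.1.1.2 and Appendix C so that 6.4 either contains or cross-references every mandatory stop, with the same force and the same statement on permanence wherever it appears. In doing so:

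- settle the status of the gallstone rules (suspected and confirmed) in 6.4;
- settle the status of the pancreatic cancer rule in 6.4, and say whether it applies to both arms or only to treatment containing a GLP-1 receptor agonist;
- align the calcitonin wording in both bands, and say whether the time limit on suspected medications includes trial product.

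The sponsor's clinical team decides the content of each rule. The follow-up pathway to V32A needs no change. The cost is protocol wording in the next amendment and a notification to sites; no analysis, sample size or data collection changes.
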